Enrollment Criteria. Overweight/obese men and women are the ideal study population because of its close association with NASH (6, 10-14, 65). Obese/overweight participants will be required to meet these **inclusion criteria**: a) overweight/obese ($BMI = 28-40 \text{ kg/m}^2$), b) 18-50 y of age, c) fasting glucose $< 126 \text{ mg/dL}$, d) normotensive (blood pressure $< 140/90 \text{ mmHg}$), e) non-dietary supplement user, f) nonsmoker. We will also enroll age- and gender-matched healthy adults who meet the following criteria: a) normal weight ($BMI 19-24 \text{ kg/m}^2$), b) 18-50 y of age, c) normoglycemic ($< 100 \text{ mg/dL}$), d) normolipidemic (total cholesterol $< 240 \text{ mg/dL}$ and triglyceride $< 150 \text{ mg/dL}$), e) normotensive (blood pressure $< 140/90 \text{ mmHg}$). Those having any of these **exclusion criteria** will not be enrolled: a) regular tea drinkers (*Camellia sinensis* or herbal varieties; ≥ 2 cups/wk), b) vegetarians, c) use of any medications to manage diabetes, hypertension, or hyperlipidemia (e.g. statins, metformin, ACE inhibitors), d) use of any medications known to be contraindicated for use with green tea ingestion (e.g. antipsychotic medications [Clozapine, lithium, Diazepam]), blood

thinning medications [Warfarin]), e) user of dietary supplements, prebiotics or probiotics, f) recent use of antibiotics or antiinflammatory agents, g) women who are pregnant or lactating, or have initiated or changed birth control in the past 3-months, h) individuals with any gastrointestinal disorders or surgeries, i) hemochromatosis, j) alcohol intake > 3 drinks/day, k) any history of cancer.

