Overview of Study Procedures. Potential participants who call the study center in an anonymous manner for more information as well as those identified through ResearchMatch will be given a brief description about the study and asked a few questions to determine their eligibility (see *Phone Script* attachment). If they meet the eligible criteria, they will be invited to the study center for a screening meeting. During the meeting, the Informed Consent (see *Informed Consent* attachment) will be explained and provided for them to review. The participant will then be given the opportunity to review the Informed Consent form. If he/she chooses to participate in the study, they will then be asked to provide written consent. Women choosing to participate will also be asked to self-administer a urinary pregnancy test. If women self-report that the pregnancy test is negative, they will continue with the screening process. After receiving informed consent, the participants' height, weight, waist circumference, and blood pressure will be measured. Additionally, a small fasting blood sample will be collected to blood chemistry analysis. If they are not fasted at least 10 hours), they will be asked to come back in the fasted state at time of mutual convenience. These blood results in combination with anthropometric parameters will determine the participant's eligibility.

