Eligible participants who agree to proceed with the study will be invited to meet with a registered dietitian or trained research personnel who will instruct them on how to complete a dietary food record, explain the details regarding following a low-polyphenol diet throughout the intervention, and provide instruction of foods to avoid prior to the pharmacokinetic trial at wk 0. Prior to the initial pharmacokinetics trial, participants will be asked to collect 3 days of fecal samples and return to the study center to participate in a sugar probe test. After completing the sugar probe test, participants will return to the study center at least 3 days after to complete a 12-h pharmacokinetics trial. Afterwards, participants will be provided a 2-wk supply of GTE-rich or placebo confections. After 2 wk, fasting blood will be collected from the participants and the other 2-week supply of confections will be provided for the remainder of the study. Upon completing the 4-week intervention, participants will complete a second sugar probe test. We estimate that completion of all study procedures will take 6-8 wk per participant. Each step of the study procedure will be discussed in detail below. See *Study Design* attachment for an overview of the study.

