Screening Meeting. Potential participants who have met the initial criteria of the study (based on the telephone interview) will be invited to the study center at a mutually convenient time. During this time, the participant and a member of the research team will meet in a private, quiet conference room or office. The individual will be provided the informed consent form, and its contents will be described to the potential participant. The participant will then have the opportunity to review it, and if they choose to participate in the study, they will be asked to provide written consent. Although the participant will be asked to sign the informed consent, the participant will be told that they will not be asked to participate if their body measurements, blood pressure, or plasma chemistries (see *Enrollment Criteria*) do not meet the study criteria. All female participants will be asked to undergo a self-administered pregnancy test using a pregnancy urine test strip to ensure that only non-pregnant women are included in the study. If the participant has provided consent, we will then measure the participant's height, weight, waist circumference, and blood pressure. Next, if the participant is fasted for at least 10 hours, we will ask if a trained individual can draw a small blood sample (10 mL; 1 tube) so that we may measure blood chemistries (glucose, cholesterol, triglyceride). All samples will be coded to maintain participant anonymity. If the participant's anthropometrics, blood pressure, or plasma chemistries do not meet the study criteria, they will be told that do not meet the study criteria.

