
Intervention Phase / Test Confections. After completing the pharmacokinetics trial, participants will partake in a 4 wk intervention. Participants will be block randomized to receive a GTE-rich or placebo (no GTE containing) confection. Confections will be low carbohydrate and low calorie. Each serving (6 g) provides <15 kcal, while delivering 1 g of decaffeinated GTE. The catechin profile (82% catechins (w/w); 63% EGCG, 18% EGC, 10% ECG, 9% EC) is similar to that of freshly brewed green teas. Sucrose will be the main carbohydrate source because sugar alcohols alter microbiota composition (66) and would confound interpretation. Decaffeinated GTE was chosen to minimize potential side effects to prevent excess caffeine consumption or caffeine/drug interactions that could result during comorbidity management of metabolic conditions. Placebo confections will be identical to GTE-rich confections, but without GTE. Confections will be packaged in single-serve, oxygen impermeable containers, and coded for study blinding. Participants will be asked to store the confections in the refrigerator to maintain quality and freshness.

Participants will be asked to consume 6 confections each day (2 with each meal) for 4 weeks. Consumption of 6 GTE-rich confections is equivalent to delivering 1 g GTE/d. Participants will receive a 2-wk supply of confections after completing the pharmacokinetics trial. Halfway through the intervention (wk 2), participants will visit the study center in a fasted state (10-12 h). Participants will return any leftover confections. After a 5 min stabilization period, a single fasting blood sample will be collected following procedures stated above. After collecting blood, the participants will be provided the final 2-wk supply of confections. At the conclusion of the intervention phase (wk 4), participants will perform a second sugar probe test. Compliance will be evaluated based on the number of confections returned throughout the study.

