Sampling Handling. During the pharmacokinetics trial, at each time point, a blood sample (20 mL; 1.4 tablespoons x 10 time points = 200 mL or 0.85 cups) will be collected into evacuated blood collection tubes. Collecting a total of 200 mL or 0.85 cups at the pharmacokinetics trial is necessary to ensure adequate amount of plasma for each time point to accurately analyze the green tea catechin metabolites over the 12-hour period. During blood collection, participants may feel an initial pain when inserting the needle, bruising around the insertion area, lightheadedness, or fainting, which are common when donating blood. However, we do not foresee any additional significant risks for collecting this amount of blood over 12 hours, other than the risks stated previously.

Throughout the span of the study (~6-8 weeks in duration depending on participant/investigator availability) which consists of one acute ingestion of GTE-rich confections, a blood collection at wk 2 and 4, and 1 screening day, we will be collecting a total of ~255 mL or ~1.08 cups) of blood. Urine will be collected in provided containers (VWR) containing 10% thymol to inhibit bacterial growth. Feces will be collected using a commercial commode specimen collection system (Fisher Scientific). Briefly, the collection kit consists of the necessary materials (e.g. disposable spatula, gloves, waste bag) for participants to easily and hygienically collect their stool without contaminating the sample or themselves. We will provide participants with coolers with ice to store their fecal samples for up to 24-h after collection. We will then have the participants return their fecal samples to the study center or coordinate with study personnel to meet at a public and mutual location to return their samples within 24-h after collection. Volumes of urine will be recorded and fecal mass and observations will be recorded based on the Bristol Stool Chart (85).

During each blood collection, plasma and white blood cells will be obtained by centrifugation, and then transferred to cryogenic storage tubes. Serum samples will be obtained by allowing the blood to clot, followed by centrifugation and transfer to cryogenic storage tubes. Tubes will be

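### Pregnancy is checked once, by a self-reported strip at screening, a derived 1.4 to 4 weeks before the first GTE confections, so non-pregnancy at first exposure is not verified

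*Combined protocol and SAP*

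**What the plan says.** Section III.B, Enrollment Criteria, exclusion g) rules out "women who are pregnant or lactating, or have initiated or changed birth control in the past 3-months". It gives no time point at which this is to be re-checked.

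Section III.D, Screening Meeting, has every woman test herself at that visit. The stated method and aim are "using a pregnancy urine test strip to ensure that only non-pregnant women are included in the study". The Overview of Study Procedures in the same section says how the result is used: "If women self-report that the pregnancy test is negative, they will continue with the screening process". Neither place has study staff read or record the strip.

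On timing, the Overview says: "We estimate that completion of all study procedures will take 6-8 wk per participant". The Sampling Handling paragraph gives the same span and counts within it "a blood collection at wk 2 and 4, and 1 screening day", so the 6-8 weeks include screening. The Intervention Phase paragraph sets the exposure period: "Participants will be asked to consume 6 confections each day (2 with each meal) for 4 weeks".

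First exposure comes earlier than the daily confections. The Pharmacokinetics Trial paragraph has participants eat three GTE-rich confections (0.5 g GTE) at week 0, and draws no distinction by arm. Blood is taken at ten time points that day, 20 mL each.

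**The concern.** An exclusion criterion should hold when the participant is exposed, not only when she is screened. Here the single check comes at the first visit, and several steps follow before anything is eaten: the results call, the dietary meeting, stool collection, the first sugar probe test and a further gap. A woman who conceives in that interval, or who conceived too recently for the screening strip to show it, meets exclusion g) at first exposure, and no described step would reveal it.

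As the text stands, the week-0 exposure reaches women in both arms, and the same visit takes 200 mL of blood over 12 hours. There is a smaller statistical stake. With 20 participants per health group and two arms, a cell holds about 10 if allocation is equal within each health group (an assumption). A pregnancy discovered later could cost one of those 10.

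**Working it through.** **1. Where the check falls.** The Test Trials paragraph counts six visits, including the screening and dietary meetings. Set against the visit descriptions in Section III.D:

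| Visit | Main procedures | Pregnancy check described |
|---|---|---|
| 1. Screening | Consent, strip, measurements, fasting blood | Yes, self-reported |
| 2. Dietary meeting | Diet and collection instructions | No |
| 3. Sugar probe test, week 0 | Sugar drink, 24-h urine | No |
| 4. Pharmacokinetics trial | First GTE confections, 200 mL blood | No |
| 5. Week 2 | Fasting blood, second supply | No |
| 6. Week 4 | Second sugar probe test | No |

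The Overview places the strip before the screening blood draw and asks a woman who is not fasted to return later. The strip can therefore predate even the screening chemistry.

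**2. Interval from strip to first GTE.** The protocol states no such figure, so there is nothing to reproduce; it has to be derived.

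Interval = total duration - intervention - closing procedures.

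Inputs: total 42-56 days (6-8 weeks, Overview); intervention 28 days, starting straight after the pharmacokinetics trial; closing procedures 0 days, 1 day (24-h urine of the second sugar probe test) or 4 days (if the 3-day stool collection also falls after week 4).

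| Closing procedures | 6 weeks total | 8 weeks total |
|---|---|---|
| 0 days | 42 - 28 - 0 = 14 days | 56 - 28 - 0 = 28 days |
| 1 day | 42 - 28 - 1 = 13 days | 56 - 28 - 1 = 27 days |
| 4 days | 42 - 28 - 4 = 10 days | 56 - 28 - 4 = 24 days |

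The range is 10-28 days: 10/7 = 1.4 weeks to 28/7 = 4.0 weeks. Adding the 28 days back, the same strip has to cover dosing up to 38-56 days after screening.

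**3. Lower check from the quantified steps.** The 3-day diet record and stool collection plus a 3-day gap after the sugar probe test make 6 days. Adding 2-3 days (assumed) for notice of eligibility gives 8-9 days. Scheduling delay would have to supply the rest. The gap itself is inconsistent: the Overview and Test Trials paragraphs make it at least 3 days, the Pharmacokinetics Trial paragraph within 3 days. These must be reconciled, but they move the interval by days only.

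**4. Size of the risk.** The documents give neither the number of women nor a conception rate, so this is illustration on assumed inputs. With n women, monthly conception probability q and w weeks, p = 1 - (1 - q)^(w/4.345), and the chance of at least one conception between strip and first dose is 1 - (1 - p)^n.

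- n = 10, q = 0.1%, w = 2: about 0.5%.
- n = 20, q = 0.5%, w = 2 to 4: about 4.5% to 8.8%.
- n = 30, q = 2%, w = 4: about 43%.

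The calculation leaves out early pregnancies missed by the strip and misreported results.

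**The case against.** The strongest reply is that the stated aim concerns who is included in the study, and the protocol does check that at inclusion. Nothing promises a check at first dose, so no statement is contradicted. This stands. A reader might infer that the aim fails at dosing, or that pregnant women will be given GTE. The text supports neither; it supports only that status at first exposure is not verified.

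Second, the interval is inferred from an estimated total that depends on availability, and the quantified steps alone need far less than 4 weeks. That is fair, and it is why the range is given and labelled as derived. The absence of any stated maximum remains.

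Third, a reader might infer that the trial requires no contraception. That cannot be established: the consent form and phone script are not available and could contain such instructions. One can say only that the text shown describes none.

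Fourth, the protocol gives no reason for exclusion g) and states no pregnancy-specific hazard of the confections. True, but the criterion is the sponsor's own, and whatever its reason it is of little use if it no longer holds at exposure.

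Last, a repeat strip shares the blind spot of the first for very recent conception, and leaves the following 4 weeks unchecked. Both limits are real. They bound the benefit of a repeat without removing it.

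**Conclusion.** The point holds in a limited form. Pregnancy status is established once, by self-report, at screening. About 1.4-4 weeks then pass before the first GTE confections, with no maximum set and no later check described in the text shown. Followed exactly as written, the plan allows a woman who meets exclusion g) by then to be dosed; it does not show that this would happen.

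The interval rests on the 6-8 weeks including screening, as the Sampling Handling paragraph indicates, and on 0-4 days of closing procedures. The probability of an event cannot be pinned down: the illustrative range of 0.5% to 43% reflects assumed inputs and supports no claim about frequency. The case for acting rests on the low cost of closing most of the gap before first exposure. The point does not bear on the power calculation or the primary analysis.

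**What to change.** Repeat the protocol's existing urine strip when each woman arrives for the week-0 pharmacokinetics visit, before the first blood draw and the first confection. Have study staff record the result, and apply the existing exclusion g) to it. Add a line to the Pharmacokinetics Trial paragraph and to the consent form. If the consent form or phone script already covers a re-check or pregnancy reporting, refer to it in the visit descriptions.

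The cost is one strip and one extra urine void per woman, plus the wording. The void is a genuine addition, because all urine scheduled at that visit is collected after ingestion. The visit itself is already planned, and no dose or schedule changes.

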Potential participants who meet the criteria, will be contacted within a few days after their screening meeting to provide them with their blood and body measurement results and inform them of their eligibility to participate in the study. Consistent with our CLIA exemption, blood results will be provided in a categorical manner (i.e. “normal”, “marginally high”, “high”) rather than providing actual blood concentrations of lab values (see *Subjects Results Sheet*). Potential participants having any blood values outside of the “normal range” will be directed/encouraged to follow-up with their own physician. Those having body measurements, blood pressure, and blood values within acceptable limits (see Inclusion/Exclusion criteria), will be invited to participate in the study. Subjects will be included or excluded based on a best fit of the inclusion and exclusion criteria (an example of best fit would be if a potential subject's BMI is 27 kg/m², which is outside the specified BMI inclusion range for overweight/obese participants they might still be included in the study if they meet all other inclusion and exclusion criteria more closely than other potential subjects). Participants will be read one phone script if they qualify and another phone script if they do not qualify (see *Participant Eligibility Phone Script* attachment). Potential participants who qualify for the study will be communicated a message as follows: I have your screening results. “Congratulations, you meet the eligibility criteria for our clinical trial. Your body measurements, blood pressure, and fasting blood chemistries of glucose, triglyceride, and cholesterol were all within the specified range. Your glucose falls in the [category], triglyceride falls in the [category], and cholesterol falls in the [category]. A summary of your results has been prepared for you, which you will receive when you come in for your trials. We look forward to and are thankful for your participation.” Potential participants who do not qualify will be provided the following message: “I have your screening results. Unfortunately, you do not meet the eligibility criteria for our clinical trial. Your body measurements, blood pressure, glucose, triglyceride, and/or cholesterol were not within the eligible range. Your glucose falls in the [category], triglyceride falls in the [category], and cholesterol falls in the [category]. A summary of your results has been prepared for you. Please let me know if you would like to drop by the study center to collect a hard copy of your information or if you would like them emailed to you. Thank you so much for your time and effort.” All individuals regardless of study eligibility will be encouraged to consider sharing these results with their physician.

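### The best-fit enrolment rule contradicts the mandatory eligibility criteria, and the nonsmoker criterion is written for the obese group only

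*Combined protocol and SAP*

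**What the plan says.** **Fixed rules.** Enrollment Criteria (III.B) opens the obese/overweight list with "Obese/overweight participants will be required to meet these" and then gives the inclusion criteria, the first being BMI 28-40 kg/m². The exclusion list applies to everyone: those with any item on it "will not be enrolled: a) regular tea drinkers", and so on to item k.

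**What candidates are told at consent.** Screening Meeting (III.D) says candidates will be informed that "they will not be asked to participate if their body measurements, blood pressure, or plasma chemistries" fail the study criteria. The same section has women take a pregnancy test "to ensure that only non-pregnant women are included in the study".

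**The best-fit rule.** Later in Screening Meeting, one sentence reads: "Those having body measurements, blood pressure, and blood values within acceptable limits (see Inclusion/Exclusion criteria), will be invited to participate in the study". The next reads: "Subjects will be included or excluded based on a best fit of the inclusion and exclusion criteria". The example is a person with BMI 27, which the protocol itself describes as out of range; of such people it says "they might still be included in the study if they meet all other inclusion and exclusion criteria more closely than other potential subjects".

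**The qualifying message.** Everyone who qualifies hears the same script, which includes: "Your body measurements, blood pressure, and fasting blood chemistries of glucose, triglyceride, and cholesterol were all within the specified range".

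**Smoking.** Nonsmoker is item f of the obese/overweight list. The healthy list (items a to e: BMI, age, glucose, lipids, blood pressure) has no smoking item, and neither do the shared exclusions (a to k). Recruitment (III.B) gives a smoking question as one example from the scripted phone interview, without saying how the answer is used for each group. Matching is on age and gender. The main model, in Power Calculation and Data Analysis (III.B), names health status, gender, treatment and their interactions.

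**The concern.** The first problem is that two rules govern the same decision. Under Enrollment Criteria, a candidate with BMI 27 is ineligible for the obese group. Under Screening Meeting, the same candidate may be enrolled. The only stated condition is relative, so the outcome depends on who else happens to have been screened, and there is no limit that two members of staff could apply alike. The sentence also names the exclusion criteria, which Enrollment Criteria treats as absolute.

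The second problem is that the two health-status groups are selected by different written rules on smoking. Objective 1 compares catechin pharmacokinetics between obese and healthy adults. Health status is not randomised, so any factor allowed in one group and barred in the other is a possible confounder. What is at stake is the reading of that comparison and a clear account of who was enrolled.

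**Working it through.** **1. The BMI example, passage against passage.**

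| Place | Rule | BMI 27 candidate |
|---|---|---|
| Enrollment Criteria | BMI 28-40 is mandatory | Not eligible |
| Screening Meeting, consent | Told that failing a measured criterion means no participation | Statement untrue if enrolled |
| Screening Meeting, best fit | May enter if otherwise a closer fit than others | May be enrolled |
| Screening Meeting, qualifying message | Told that body measurements were in range | Statement untrue |

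Since 27 < 28, the first and third rows cannot both hold. The second and fourth follow whenever the best-fit rule is used for a measured value.

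**2. Smoking, list against list.** Obese inclusion list: yes (item f). Healthy inclusion list: no. Shared exclusions: no. The other example phone question, on supplements, is backed by shared exclusion e, so it binds both groups. The smoking question has no such backing for healthy callers.

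**3. Illustrative size.** The documents give no SD, no count of off-criteria entrants, no number of healthy smokers and no smoking effect. Every input below other than the stated 80% power, the alpha, the group sizes and the BMI ranges is an assumption.

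*Set-up.* Two-sided alpha 0.05, noncentral t, an assumed 10 per treatment arm within each health group, 36 df. In SD units, the standard error of the obese contrast is √(2/10) = 0.447 and that of the interaction is √(4/10) = 0.632. Taking no effect in healthy adults, the stated 80% interaction power is met at d = 1.82. The obese contrast then has 97.7% power, consistent with the stated figure of more than 90%.

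*BMI.* Assume the effect rises linearly from 0 at BMI 21.5 to full at BMI 34, the midpoints of 19-24 and 28-40. The fraction of full effect is (28 − 21.5)/12.5 = 0.52 at BMI 28 and (27 − 21.5)/12.5 = 0.44 at BMI 27. With k of 20 obese participants at that BMI, split equally between arms, the mean effect is multiplied by 1 − (k/20)(1 − fraction). The comparison is between k people at BMI 27 and k people at the lowest eligible value, 28, so the starting powers are already below 80%.

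| k | Multiplier, BMI 28 → 27 | Interaction power | Contrast power |
|---|---|---|---|
| 2 | 0.952 → 0.944 | 76.0% → 75.3% | 96.5% → 96.2% |
| 4 | 0.904 → 0.888 | 71.6% → 70.1% | 94.7% → 94.0% |

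If the line starts at BMI 24 instead, interaction power goes from 74.9% to 74.0% (k = 2) or from 69.3% to 67.3% (k = 4). The obese mean BMI falls by 2/20 = 0.1 or 4/20 = 0.2 kg/m², which is 0.8% or 1.6% of the 12.5 between midpoints. Because the best-fit rule has no limit, this covers only the protocol's own one-unit example.

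*Smoking.* Compare 20 with 20, 38 df, standard error √(2/20) = 0.316 SD, no adjustment. If smoking shifts an outcome by 0.3 to 0.8 SD and k healthy participants smoke, the bias is (k/20) × 0.3 to 0.8 SD.

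- k = 2: bias 0.03 to 0.08 SD, false-positive rate 5.1% to 5.7%.
- k = 6: bias 0.09 to 0.24 SD, false-positive rate 5.9% to 11.5%.

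**The case against.** The best-fit rule is disclosed and looks deliberate: the protocol openly calls BMI 27 out of range and describes a way of choosing among candidates. That is so, but Enrollment Criteria neither refers to it nor allows for it, and disclosure does not supply a limit.

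The conflict can also be drawn too widely. The sentence inviting those within acceptable limits does not say that nobody else may be invited, so it does not by itself contradict the next one. The consent passage reports what candidates are told; it is not an enrolment rule. Both objections stand. The direct contradiction is between Enrollment Criteria and the best-fit sentence, and the consent statement matters because it would become untrue.

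A reader might infer that any exclusion, such as a barred drug or a disease, could be waived. The documents do not support that. The only example is a one-unit BMI miss by someone who fits everything else well, and the protocol insists that only non-pregnant women enter. What stands is that the sentence names the exclusion criteria without saying which of them are closed.

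A reader might also infer that healthy smokers will be enrolled. That is not shown. Callers are asked about smoking, only those who pass the phone screen are invited, and the unseen script may turn smokers away from both groups. The plan also allows regression with potential covariates, although smoking is not named. What can be shown is an unequal written list, not an unequal cohort.

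Finally, the numerical illustrations rest on assumed inputs. The 11.5% figure needs 6 smokers among 20 healthy adults, a 0.8 SD effect and no adjustment; the documents support none of these. This objection stands in full.

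**Conclusion.** The point holds as a minor one. Two things are certain from the text: the mandatory BMI range and the best-fit example cannot both be followed, and the nonsmoker criterion is missing for the healthy group. It is equally clear that the qualifying message would be wrong for an entrant like the protocol's own example.

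Confounding of the obese-versus-healthy comparison by smoking is possible, not established. It depends on whether healthy smokers would pass the phone screen, which the documents do not show.

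A reader might take either point as a threat to the primary GTE-versus-placebo contrast in obese adults. It is not: treatment is randomised, so neither point confounds that contrast. Loose entry rules mainly change whom it describes.

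The size is unknown and probably small. On the assumptions shown, a few BMI 27 entrants in place of BMI 28 cost at most about 2 points of interaction power (69.3% to 67.3%). These figures indicate scale only and are not estimates for this trial.

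**What to change.** - In Enrollment Criteria, state one smoking criterion that applies to both the obese and the healthy group, and make the Phone Script follow it.
- Reconcile Screening Meeting with Enrollment Criteria and with the consent statement. Say that best fit does not reach the exclusion criteria, and write any BMI latitude as a fixed numeric range in the inclusion criterion itself.
- Reword the qualifying phone message so that it is true for everyone who receives it.

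The cost is a few lines of protocol and script wording. Recruitment may be slightly slower if borderline candidates or healthy smokers are turned away.
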